- 2. Proforma for collection of information from study subjects(baseline survey)
- 3. Behavioural Change Communication(BCC) material
- 4. Booklet for mother
- 5. Fortnightly Pneumonia surveillance tool (Diary).

Operational Definition of Community Based Interventions (CBI): These are Behavioural Change Communication (BCC) activities conducted by ASHA/Anganwadi worker (AWW) for mothers of under five children with respect to following domains:

- 1. Child feeding practices which include exclusive breast feeding and appropriate weaning.
- 2. Immunization of under five children.
- 3. Indoor air pollution (reduction in use of biomass fuel and smoking).
- 4. Hand hygiene of mother/care taker of child: Correct hand washing steps at following 4 occasions: After defecation, after cleaning child's bottom, before food preparation, before feeding the child.
- 5. Knowledge Attitude and Practices of mother about pneumonia: Signs and symptoms of pneumonia, danger signal of severe disease and appropriate care seeking.
- 6. Cough etiquettes.

The BCC activities will include interpersonal communication, group discussions and demonstration etc. Outcome of these Community based interventions will be measured in children i.e. incidence and also deaths due to pneumonia.

Study duration: Two years.

Methodology:

The study will be conducted in phase wise manner. The activities in different phases are listed below:

Phase 1: Preparation (2 months)

- 1. Development and validation of research tools: Tools as described above will be developed and used for data collection. These tools will be quantifiable and objective. The team of investigators including paediatrician, biostatistician and anthropologist/social scientist will be involved in development and drafting of study tools. While preparing the tools available training booklets will be extensively used. All the tools will be bilingual and will be piloted for validity, question framing, relevance, sequencing and time required for filling the tools. The tools then will be finalized after making necessary modifications.
- 2. Appointment of Field supervisor (FS) and training. Training of FS
- 3. Baseline data in brief and with limited objectives will be collected from all clusters prior to randomizing them into intervention and control clusters.

Objectives of baseline survey:

- a. To obtain basic socio-demographic information of the family (age, sex, income, education & occupation)

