- b. To determine proportion of women in reproductive age group

- c. To determine incidence of pneumonia in last one year and incidence of ARI in last one month and also to measure child mortality in last one year including mortality due to pneumonia.
- d. To determine sources contributing to indoor air pollution like type of fuel used for cooking, smoking by family member, overcrowding.
- e. To measure proportion of other risk factors like low birth weight, birth order, malnutrition, breast feeding, immunization status of under five year old and KAP of mother about pneumonia including care seeking behavior.
- 4. Intervention cluster will be geographically separated so as to reduce contamination. There are minimal chances of contamination however some may occur during nonformal communication of ASHA AWW with each other.
- 5. Identification and orientation of private medical practitioners, concerned Taluka Health Officer, Medical Officers, Auxiliary Nurse Midwives (ANM).
- 6. Accredited Social Health Activist (ASHA), Anganwadi workers (AWW) from the selected clusters will be identified and they will be incentivized through the project.

Field supervisors will be trained regarding

- a. Introductory contents pertaining to pneumonia: protocol specific training, IMNCI guidelines for ARI/Pneumonia, diagnosis and standard management of pneumonia, problem statement of ARI/Pneumonia in their area.
- b. Intervention related training: Relevance of selected risk factors in reduction of pneumonia. Methods to reduce the same through Behavioural Change Communication activities.
- c. Surveillance related supervisory training:
- d. Communication skills and conducting session for mothers above mentioned areas. Over and above their role as a supervisor will be explained and taught to them.
- e. Initial Training: Two days and one additional day for hands on training in the field. The material intended to be used by them for Behavioural change communication (BCC) during interpersonal communication with mothers will be shared with them and their competency will be assessed in the field through demonstration of conducting a BCC session for mothers.

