Phase 2: Baseline/Enrolment (3 months): Enlisting of study subjects in intervention and comparison clusters. This will be done through house to house visits by ASHA/AWW in their respective cluster. Written informed Consent will be taken from mother by ASHA/AWW In first visit following details will be obtained after informed consent.

- a. Basic socio demographic information(will be collected prior to randomising them into intervention and control cluster)
- b. Enlisting all mothers of under five children and expectant mothers.
- c. Enlisting all under five children
- d. Selection and random allocation of the clusters to intervention and comparison arm

All the data collected will be entered in predesigned excel sheet and database will be generated for further analysis.

Phase 3: Intensive Community based Intervention (4 months)

1. First round of BCC activities for mothers: This will be conducted by the trained and equipped Field supervisor in small groups consisting of about 10 mothers. Every week she will conduct one session for about 10 mothers in anganwadi /community hall in intervention clusters only. Some of these sessions will be attended by investigators. All mothers in her cluster will be educated in two months.

The content of BCC activities will be

- Child feeding practices which include exclusive breast feeding and its distinctive advantages and appropriate weaning.
- Role of Immunization of under five children in preventing various vaccine preventable diseases.
- Hazards of biomass fuel and use of substitutes like smokeless chulla, LPG etc.
- Hand hygiene of mother/care taker of child: Correct hand washing steps at following 4 occasions: After defecation, after cleaning child's bottom, before food preparation, before feeding the child.
- Knowledge, Attitude and Practices of mother about pneumonia: Signs and symptoms
 of pneumonia, danger signal of severe disease and appropriate care seeking, timely
 contact by mother or care taker to the ASHA/AWW etc.

BCC material in local language developed especially for mothers will be handed over to them. This material will help mothers to adopt practices which will minimize risk factors of pneumonia. Subsequently enrolled subjects (delivered women, newborns, including migrated) will also be receive BCC activities in a special session.

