Pneumonia: child with cough or difficulty in breathing as having pneumonia.

severe pneumonia: If the symptoms are associated with lower chest wall in drawing or subcostal retraction,

Very severe pneumonia: If there is a danger sign such as central cyanosis, or severe respiratory distress, convulsion, inability to rouse the child or if the child is unable to drink.

Interval: An episode of pneumonia after 7 days of previous episode will be counted as a new episode.

If answer is yes then ASHA/AWW will enter the information in the diary maintained by her and submit information to site investigators(SI). They will confirm the pneumonia using WHO IMNCI protocol.

Appropriate management of child's illness will be ensured. This record will be submitted in fortnightly meeting (one will coincide with their monthly meeting) with FS and the same will be updated periodically. In addition, information about any death among under five children will be collected and the cause of death will be ascertained.

Continued intervention: Will be given by field supervisor (FS) through monthly house to house visits During her house to house visits in intervention arm FS will interact with all mothers and enquire about practicing the methods, skills steps learnt during intensive intervention. In case of unsatisfactory response FS will reinforce the knowledge and skills.

The sub investigator will supervise a pair of cluster from intervention and comparison arm and will do surprise home visit to cross check information collected by AWW/ASHA.

In comparison clusters ASHA/AWW will continue their role as per existing guidelines and collect information about pneumonia and deaths due to pneumonia through fortnightly house to house visits and submitted to FS fortnightly. And AWW and ASHA will continue to

promote all activities that are part of national programme (immunisation, optimal feeding practices) in control sites.

Midterm evaluation of the project will be done by third party at the end of three months of surveillance.

Detection and referral of pneumonia cases is a part of routine activity of ASHA/AWW workers so stopping of these duties is not advisable. And they will be closely monitored by field supervisors and sub investigators.

Standard care for ARI / Pneumonia will be provided to referred children through our own institutions and partner in public sector in two districts.

Phase 5: Data Analysis (2 months) and Final Report writing (1 month)

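### Field supervisors are trained in the intervention before clusters are allocated, and comparison-arm workers then report to this cadre; the protocol's contamination statement does not cover that route

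*Protocol*

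**What the plan says.** **Training comes first.** The Protocol's Phase 1 (Preparation), item 2, is "Appointment of Field supervisor (FS) and training. Training of FS". The curriculum in the same phase is common to all field supervisors, with no distinction by arm. Item b covers the intervention, including "Methods to reduce the same through Behavioural Change Communication activities". Item d covers communication skills and running sessions for mothers. Item e adds a hands-on day, at which "their competency will be assessed in the field through demonstration of conducting a BCC session for mothers".

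**Allocation comes second.** Phase 2 (Baseline/Enrolment), item d, is "Selection and random allocation of the clusters to intervention and comparison arm". The timeline also lists supervisor training under Phase 1 and randomisation of clusters under Phase 2.

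**Delivery is restricted by arm.** Phase 3 places the group sessions "in anganwadi /community hall in intervention clusters only". Phase 4 places the supervisors' monthly home visits in the intervention arm.

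**The reporting line reaches both arms.** In comparison clusters, under Phase 4, workers "collect information about pneumonia and deaths due to pneumonia through fortnightly house to house visits and submitted to FS fortnightly". Phase 4 also has field supervisors and sub-investigators closely monitoring the workers, without limiting this to one arm.

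**Contamination.** Phase 1, item 4, relies on geographic separation and states: "There are minimal chances of contamination however some may occur during nonformal communication of ASHA AWW with each other".

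**The concern.** The comparator is meant to be existing practice. Contamination is described as a matter of workers talking to one another, and distance is the only safeguard. Distance does little against a route that runs through project staff whose role touches both arms.

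Two features create such a route. First, when a supervisor demonstrates a BCC session in the field, no cluster yet has an arm, and no text keeps the demonstration out of clusters that may become comparison clusters. Second, comparison-arm workers report for a year to staff trained to promote the intervention, and nothing tells those staff to withhold its content.

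If some BCC content passes this way, the contrast between arms shrinks and the trial underestimates the effect. With 8 clusters per arm there is little precision to spare.

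**Working it through.** **1. Order of work.** Supervisor training is in Phase 1 and allocation in Phase 2. Phase 1, item 3, also puts the baseline survey before randomisation. At the time of the demonstration the arms are therefore unknown, and demonstrating only in intervention clusters is not possible.

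**2. Which supervisors are BCC-trained.** There is one curriculum and it precedes allocation. If supervisors are shared between arms, the person who delivers BCC also receives comparison records. If they are arm-specific, those serving comparison clusters have still had items b and d. On either reading, comparison workers report to BCC-trained staff. At one submission a fortnight that is 52/2 = 26 submissions a year; the protocol does not say whether each is a face-to-face meeting.

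**3. Possible dose from a demonstration.** The site is not given. Assume a demonstration takes place in a candidate cluster picked at random. There are 47 candidates, of which 16 enter the trial, 8 per arm.
- Chance that it is a future comparison cluster: 8/47 = 17%.
- Chance that it is outside the trial: 31/47 = 66%.

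If the group has about 10 mothers, as in Phase 3, with one child each, it covers 10/300 = 3.3% of an average cluster. This part of the route is small.

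**4. Dilution.** The protocol plans an incidence of 0.30 and a 50% reduction, so 0.30 × (1 − 0.50) = 0.15. Let L be the share of the effect that leaks. The protocol gives no value for L, so it is assumed here.
- Comparison incidence: q = 0.30 − 0.15L.
- Rate ratio seen: 0.15/q.

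**5. Power, as illustration.** Take c = 8 clusters per arm, m = 300 children per cluster, two-sided alpha 0.05 (assumed, as none is stated) and between-cluster coefficient of variation k:

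z = (q − 0.15) × √(c − 1) / √[(q + 0.15)/m + k²(q² + 0.15²)] − 1.96, and power = Φ(z).

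For L = 0 and k = 0.5: the bracket is 0.45/300 + 0.25 × 0.1125 = 0.029625; √(7 × 0.0225/0.029625) = 2.306; z = 0.346; power = 63.5%.

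| L (assumed) | q | Rate ratio seen | Reduction seen | Power, k = 0.5 | Power, k = 0.35 (assumed) |
|---|---|---|---|---|---|
| 0 | 0.300 | 0.500 | 50.0% | 63.5% | 89.4% |
| 10% | 0.285 | 0.526 | 47.4% | 57.9% | 85.1% |
| 20% | 0.270 | 0.556 | 44.4% | 51.5% | 79.3% |
| 30% | 0.255 | 0.588 | 41.2% | 44.5% | 71.5% |
| 50% | 0.225 | 0.667 | 33.3% | 29.5% | 50.2% |

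The first row does not reproduce the protocol's 80% power with 15 clusters. With k = 0.5 the matching formula needs 1 + 7.849 × 0.029625/0.0225 = 11.3 clusters per arm, that is 12, or 24 in total. That is a separate matter. Only the change down each column bears on this point.

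**The case against.** A reader might infer that the plan itself carries the intervention into the comparison arm, or that mothers in comparison clusters are taught before randomisation. The documents do not support either reading.

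- The site, number and audience of the demonstrations are not stated. They may be practice sessions, or fall in clusters that never enter the trial.
- Group sessions and supervisor home visits are confined to the intervention arm. What comparison workers pass to supervisors is surveillance data.
- Phase 3 speaks of a supervisor's own cluster, and the section on training ASHA and Anganwadi workers refers to supervisors of the intervention arm. Supervisors may already be arm-specific; Phase 4 does not say which of them receive comparison records.
- Phase 1 also contains items that presuppose selection or allocation, so the phase lists may not be strictly chronological.
- Feeding and immunisation promotion are openly part of the comparator through the national programme.
- The leaked share has no basis in the protocol. At 10% to 20% a reduction of 44% to 47% would remain, so it goes too far to say that a null result could not be told apart from contamination.

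All of this stands as a limit on the claim. The gap remains, because the arm restriction covers formal sessions and home visits and leaves out the Phase 1 demonstrations and the contact between supervisors and comparison workers. The arm-specific reading does not remove it either, because the common training precedes allocation.

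The sub-investigator's role, "The sub investigator will supervise a pair of cluster from intervention and comparison arm", might also be read as a leak. It is better read as a strength, since the same surprise cross-check is applied in both arms.

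**Conclusion.** The concern holds as an open route, with no evidence that contamination will occur. The stated order of work trains supervisors in BCC before allocation, comparison workers report to and are monitored by this cadre, and the statement that contamination is minimal does not address it. The size is unknown and probably modest: a possible demonstration and fortnightly contact with workers are a weak dose beside two rounds of sessions and a year of monthly visits. The bias is toward no effect. At an assumed leakage of 10% to 20%, the visible reduction falls from 50% to between 47.4% and 44.4%, and power falls by about 6 to 12 percentage points at k = 0.5 (4 to 10 at k = 0.35). Higher rows of the table show the outer range only.

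This rests on supervisors being the ones who deliver BCC, as the summary, Phase 3 and Phase 4 say. The operational definition of the interventions names ASHA and Anganwadi workers instead. The change is worth making because it is cheap, although the trial does not stand or fall on it.

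**What to change.** 1. Give the intervention module (item b) and the session-running part of item d after allocation, and only to supervisors of intervention clusters. If that is not possible, hold the field demonstrations outside all 47 candidate clusters.
2. Assign each supervisor to one arm. Give supervisors in both arms identical surveillance training (items a and c), and keep the reporting route identical in both arms.
3. Hold the fortnightly record meetings separately by arm, with no BCC material at comparison meetings.
4. Amend the contamination statement in Phase 1, item 4, to name the supervisor route and these safeguards.

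Keep the sub-investigator's paired cross-check. Do not send comparison data by a different route from intervention data, because outcome collection would then differ by arm and could bias the primary outcome in a way that contamination would not.

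The cost is rostering and sequencing: less freedom to swap supervisors between clusters, and one extra training or meeting slot.

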2. Second round of BCC activities: This will be conducted for reinforcement of the information delivered in first round. It will be conducted again in small groups after 2 months of first round and completed in two months. In this round emphasis will be given on skills acquired and demonstration by participants.

Various BCC activities will be supervised by sub-investigators.

Training of ASHA/AWW:

Investigators will train AWW & ASHA from intervention arm to orient them about the objectives, importance of project and their role in the project for surveillance.

Contents of the training modules:

- a. Introductory contents pertaining to pneumonia: protocol specific training, IMNCI guidelines for ARI/Pneumonia, diagnosis and standard management of pneumonia, problem statement of ARI/Pneumonia in their area.
- b. Surveillance related training: Fortnightly surveillance, maintenance of diary
- c. Communication skills and conducting session for mothers.
 Investigators will train all AWW and ASHA from both the arms regarding surveillance. Duration of training for ASHA/AWW:One day.

ASHA/AWW/FS from intervention arm will be requested to share their mobile numbers with mothers so that in case of any need like of sickness of child mother can contact them. The importance of response to mothers call will be emphasized as it may ensure appropriate management of child's illness and prevent the mortality. Training about fortnightly surveillance will be imparted to them.

Information about available emergency services like help line 108,102 will be given and ASHA/AWW/FS will communicate their mobile numbers to mothers/expectant mothers and will appeal to contact on same whenever the child is sick.

Phase 4: Followup and continued Intervention (12 months)

Pneumonia surveillance: This will be done in intervention arm for a period of one year by AWW/ASHA in rural area and AWW in urban slums through fortnightly house to house visit and enquiring about signs and symptoms related to pneumonia in preceding fortnight. This will help to calculate the fortnight incidence of pneumonia. Fortnightly visits will be adequate to get incidence of pneumonia in addition to this the mobile numbers of ASHA will be shared to mothers so that in case of any need like sickness of child mother can contact them. This will help to record attacks of pneumonia if any between the two fortnight visits.

Following definitions from IMNCI Guidelines will be used:

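### Pneumonia episodes are ascertained differently by arm: a telephone route meant to record extra episodes is written for the intervention arm only, so the primary comparison is biased by an unknown net amount.

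*Protocol*

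**What the plan says.** The Key Outcomes section makes the incidence of pneumonia, compared between arms, the primary outcome. These parts of section 5 (Methodology) decide how an episode is found.

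- **Telephone contact.** Training of ASHA/AWW (Phase 3) states: "ASHA/AWW/FS from intervention arm will be requested to share their mobile numbers with mothers so that in case of any need like of sickness" of the child, the mother can reach them. The next paragraph says workers "will appeal to contact on same whenever the child is sick". It names no arm, but follows directly on the intervention-arm text.
- **Purpose of the calls.** The Pneumonia surveillance paragraph of Phase 4 opens with "This will be done in intervention arm for a period of one year by AWW/ASHA in rural area and AWW in urban slums". It says "Fortnightly visits will be adequate to get incidence of pneumonia", then adds the shared mobile numbers on top, with the reason: "This will help to record attacks of pneumonia if any between the two fortnight visits".
- **What mothers are taught.** The BCC sessions of Phase 3, held in intervention clusters only, cover the signs of pneumonia and timely "contact by mother or care taker to the ASHA/AWW etc".
- **Comparison clusters.** Phase 4 has their ASHA/AWW follow existing guidelines, collect pneumonia data at fortnightly house visits and pass them to the field supervisor. No telephone route is written.
- **Confirmation.** Site investigators confirm diary entries under the IMNCI protocol. This stands in the intervention-arm surveillance text and is not repeated for comparison clusters.
- **Worker training.** "Investigators will train AWW & ASHA from intervention arm to orient them about the objectives" introduces the module list, which includes IMNCI diagnosis. After the list comes "Investigators will train all AWW and ASHA from both the arms regarding surveillance".

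**The concern.** An episode can enter the intervention-arm numerator by two routes, a visit or a call, and the comparison-arm numerator by one. Teaching mothers to recognise illness and seek help is part of the intervention. Letting the resulting calls feed the primary count is a measurement choice, and it differs by arm.

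Fortnightly recall may not pick up every phoned episode, for two reasons. A child reported while ill is easier to confirm than one recalled up to two weeks later. And because an episode more than 7 days after the last counts as new, dated calls can separate two episodes that a single recall interview might merge.

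If the calls add episodes, a true reduction is understated. The missing confirmation step for comparison clusters may overstate it. With two opposing biases of unknown size, neither a positive nor a null result could be read cleanly. The protocol also specifies no record of how an episode was first reported, so the analysis could not separate the routes afterwards.

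**Working it through.** **1. Ascertainment by arm, as written**

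| Element | Intervention clusters | Comparison clusters |
|---|---|---|
| Fortnightly visit | yes | yes |
| Calls used to record episodes | yes | not written |
| Mothers taught signs and timely contact | yes | no BCC sessions |
| Site-investigator confirmation | yes | not written |
| Sub-investigator cross-check | yes | yes |
| Worker training in surveillance | yes | yes |
| Worker training in IMNCI diagnosis | yes | unclear |

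**2. Inputs**

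From the sample size section: comparison rate λ0 = 0.30 per child-year; a 50% reduction, so λ1 = 0.15; y = 300 children per cluster; coefficient 0.5, read here as the between-cluster coefficient of variation k; 80% power; at least 15 clusters, with 8 per arm used. Significance level and sidedness are not stated.

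**3. The plan's own figure**

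The formula for unmatched cluster rates is c per arm = (z_α + z_β)² × V / (λ0 − λ1)², with V = (λ0 + λ1)/y + k²(λ0² + λ1²). Some users add 1 cluster per arm.

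V = 0.45/300 + 0.25 × (0.09 + 0.0225) = 0.0015 + 0.028125 = 0.029625, and (λ0 − λ1)² = 0.0225.

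- One-sided 5%, nothing added: (1.645 + 0.842)² × 0.029625/0.0225 = 8.14 per arm, about 16 in total. With k applied to the mean rate it is 7.37 per arm, or 14.7 in total, which rounds up to the stated 15.
- Two-sided 5%: 10.33 per arm, or 11.33 with the added cluster.

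The stated figure is therefore reachable under a one-sided reading. This point does not dispute it.

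**4. Effect of extra detection in the intervention arm**

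Let d be the ratio of detection, intervention to comparison. The documents give no value, so the range is assumed. Observed rate ratio = 0.50 × d.

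Power with 8 per arm is Φ(√[m(λ0 − λ1d)²/V_d] − z_α), where V_d is V with λ1d in place of λ1. It is shown two ways: two-sided 5% with the added cluster (m = 7, z_α = 1.96), and one-sided 5% without it (m = 8, z_α = 1.645).

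| d (assumed) | Observed λ1 | Observed rate ratio | V_d | Power, two-sided | Power, one-sided |
|---|---|---|---|---|---|
| 1.0 | 0.150 | 0.50 | 0.02963 | 64% | 79% |
| 1.1 | 0.165 | 0.55 | 0.03086 | 53% | 70% |
| 1.2 | 0.180 | 0.60 | 0.03220 | 42% | 60% |
| 1.3 | 0.195 | 0.65 | 0.03366 | 33% | 49% |
| 1.5 | 0.225 | 0.75 | 0.03691 | 18% | 29% |

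The first row is the starting point before any detection difference. Its gap from 80% belongs to the sample size and not to this point.

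**5. The opposing direction**

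If unconfirmed cases inflate the comparison-arm count by a factor u, the observed rate ratio is 0.50/u: 0.42 at u = 1.2 and 0.33 at u = 1.5. With both at work it is 0.50 × d/u, so the sign of the net bias depends on whether d or u is larger. Neither is known.

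**The case against.** The strongest reply is that the calls add little. Each visit asks about the whole preceding fortnight, the protocol calls the visits adequate, and the 7-day rule limits double counting of a phoned and visited episode. If so, d is close to 1. This stands as a reason not to claim a particular size. It does not remove the difference between arms, because the protocol itself expects the calls to help record episodes. It also means that a visit-only count costs little.

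Three stronger readings are tempting, and the documents do not support them.

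- A reader might infer that only intervention-arm workers learn to diagnose pneumonia. The position of the module list suggests it, but the text then trains workers of both arms in surveillance and gives a single one-day duration. It also describes case detection and referral as routine ASHA/AWW work. The passage is ambiguous, not exclusive.
- A reader might infer that detection is certainly higher in the intervention arm and hides the effect. No detection rates are given, only a doubling (d = 2) would bring a true ratio of 0.50 to 1.00, and the confirmation imbalance may push the other way.
- A reader might infer from the opening of the Phase 4 paragraph that comparison clusters have no surveillance. The opening summary and the comparison-cluster paragraph both say that they do.

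It is also fair to say that visit-only counting does not reach every source. Mothers taught the signs may report more at the visit itself.

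**Conclusion.** The concern holds in this form: followed as written, the plan ascertains its primary outcome differently by arm. The telephone route and the taught contact probably raise the intervention-arm count and bias towards no effect. The size is not established, and the net direction is uncertain while confirmation is written for one arm only.

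Assumed detection ratios of 1.1 to 1.5 would move a true rate ratio of 0.50 to between 0.55 and 0.75. On a two-sided 5% test with the added cluster, power would fall from 64% to between 53% and 18%. On a one-sided test without it, power would fall from 79% to between 70% and 29%. These figures rest on the assumed ratios, on k = 0.5 and on test settings that the protocol does not state. They illustrate sensitivity and are not estimates. The asymmetry itself rests on the text alone and should be settled before surveillance starts.

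**What to change.** 1. Count towards the primary outcome only episodes elicited at the scheduled fortnightly visit, with the same scripted questions in both arms. An episode that was also phoned counts if the mother reports it at the visit.
2. Write one confirmation step for both arms, triggered by the visit entry, and state that it applies in comparison clusters.
3. Leave phone contact for care as planned. Add a diary flag for episodes known only from a call, and report them separately by arm.
4. State that the case-recognition and surveillance part of the worker training (IMNCI case definition and diary) is the same in both arms. This need not extend to the management content of the module, which would alter the comparison condition.
5. State for which arm the appeal to call when a child is sick is meant.

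**Cost.** One counting rule, one diary flag, common training content within the existing one-day session, and confirmation work in comparison clusters if none was intended there. A few between-visit episodes not recalled at the visit are left out of the primary count. Greater symptom recognition by taught mothers is not removed and should be reported as a limitation.
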